## 9.0 Pretreatment Events (PTEs) and Adverse Events (AEs)

### 9.1. Definitions

### 9.1.1 Adverse Event

A Pre-Treatment Event (PTE) is defined as any untoward medical occurrence in a clinical investigation subject who has signed informed consent to participate in a study but prior to administration of any study medication; it does not necessarily have to have a causal relationship with study participation.

An adverse event (AE) is defined as any unfavourable and unintended sign (including a clinically significant abnormal laboratory finding), symptom or disease, temporally associated with the use of a medicinal product, regardless of its nature, intensity, seriousness, or presumed relationship (causality) to the product or experimental procedure used.

All adverse events which occur after the first study medication intake and within 4 weeks after the treatment stop date will be considered as treatment emergent adverse events (TEAEs).

Each TEAE will be evaluated for duration, intensity, and relationship to (or association with) the study treatment (or other causes). Additionally, the actions taken (e.g., administration of treatment) and the resulting outcome of the adverse event will be indicated on the eCRF. All adverse events will be followed up until resolved or as clinically required.

All subjects will be followed-up for safety reasons, including those subjects who withdraw or stop participation due to premature termination of the study, especially if the reason for withdrawal is an AE, by means of a phone call 4 weeks after the end of the study treatment.

Any AE, which remains unresolved after completion of the trial, requires detailed evaluation and follow-up until the AE has been resolved or a reasonable explanation for its persistence is found.

If a worsening of any pathological condition that the subject had before the start of the study or medical problems that are present prior to the start of treatment but worsen during treatment occur, these must be considered as a new adverse event and will require a complete evaluation and the relevant explanation in the case report form.

### 9.1.2 Additional Points to Consider for PTEs and AEs

An untoward finding generally may:

- Indicate a new diagnosis or unexpected worsening of a pre-existing condition. (Intermittent events for pre-existing conditions or underlying disease should not be considered PTEs or AEs.)
- Necessitate therapeutic intervention.
- Require an invasive diagnostic procedure.
- Require discontinuation or a change in dose of study medication or a concomitant medication.
- Be considered unfavourable by the investigator for any reason.

Amendment 04, Final Version 1.0 Protocol No.: BB-2001-201b EudraCT No.: 2017-000877-35

> PTEs/AEs caused by a study procedure (e.g., a bruise after blood draw) should be recorded as a PTE/AE.

07/Nov/2018

Page 72 / 142

### Diagnoses vs signs and symptoms:

Each event should be recorded to represent a single diagnosis. Accompanying signs (including abnormal laboratory values or ECG findings) or symptoms should NOT be recorded as additional AEs. If a diagnosis is unknown, sign(s) or symptom(s) should be recorded appropriately as a PTE(s) or as an AE(s).

## Laboratory values and ECG findings:

- Changes in laboratory values or ECG parameters are only considered to be PTEs or AEs if they are judged to be clinically significant (i.e., if some action or intervention is required or if the investigator judges the change to be beyond the range of normal physiologic fluctuation). A laboratory re-test and/or continued monitoring of an abnormal value are not considered an intervention. In addition, repeated or additional noninvasive testing for verification, evaluation or monitoring of an abnormality is not considered an intervention.
- If abnormal laboratory values or ECG findings are the result of pathology for which there is an overall diagnosis (e.g., increased creatinine in renal failure), the diagnosis only should be reported appropriately as a PTE or as an AE.

## Pre-existing conditions:

- Pre-existing conditions (present at the time of signing of informed consent) are considered concurrent medical conditions and should NOT be recorded as PTEs or AEs. Baseline evaluations (e.g., laboratory tests, ECG, X-rays etc.) should NOT be recorded as PTEs unless related to study procedures. However, if the subject experiences a worsening or complication of such a concurrent condition, the worsening or complication should be recorded appropriately as a PTE (worsening or complication occurs before start of study medication) or an AE (worsening or complication occurs after start of study medication). Investigators should ensure that the event term recorded captures the change in the condition (e.g., "worsening of...").
- If a subject has a pre-existing episodic condition (e.g., asthma, epilepsy) any occurrence of an episode should only be captured as a PTE/AE if the episodes become more frequent, serious or severe in nature, that is, investigators should ensure that the AE term recorded captures the change in the condition from Baseline (e.g., "worsening of...").
- If a subject has a degenerative concurrent condition (e.g., cataracts, rheumatoid arthritis), worsening of the condition should only be captured as a PTE/AE if occurring to a greater extent to that which would be expected. Again, investigators should ensure that the AE term recorded captures the change in the condition (e.g., "worsening of...").

# Worsening of PTEs or AEs:

If the subject experiences a worsening or complication of a PTE after starting administration of the study medication, the worsening or complication should be recorded appropriately as an AE. Investigators should ensure that the AE term recorded captures the change in the condition (e.g., "worsening of...").

Amendment 04, Final Version 1.0 Protocol No.: BB-2001-201b EudraCT No.: 2017-000877-35

> If the subject experiences a worsening or complication of an AE after any change in study medication, the worsening or complication should be recorded as a new AE. Investigators should ensure that the AE term recorded captures the change in the condition (e.g., "worsening of...").

07/Nov/2018

Page 73 / 142

## Changes in severity of AEs /Serious PTEs:

If the subject experiences changes in severity of an AE/serious PTE, the event should be captured once with the maximum severity recorded.

#### Preplanned surgeries or procedures:

Preplanned procedures (surgeries or therapies) that were scheduled prior to signing of informed consent are not considered PTEs or AEs. However, if a preplanned procedure is performed early (e.g., as an emergency) due to a worsening of the pre-existing condition, the worsening of the condition should be captured appropriately as a PTE or an AE. Complications resulting from any planned surgery should be reported as AEs.

#### Elective surgeries or procedures:

Elective procedures performed where there is no change in the subject's medical condition should not be recorded as PTEs or AEs, but should be documented in the subject's source documents. Complications resulting from an elective surgery should be reported as AEs.

#### Insufficient clinical response (lack of efficacy):

Insufficient clinical response, efficacy, or pharmacologic action, should NOT be recorded as an AE. The investigator must make the distinction between exacerbation of preexisting illness and lack of therapeutic efficacy.

#### Overdose:

Cases of overdose with any medication without manifested side effects are NOT considered PTEs or AEs, but instead will be documented on an Overdose page of the eCRF. Any manifested side effects will be considered PTEs or AEs and will be recorded on the AE page of the eCRF.

#### 9.1.3 **Serious Adverse Event**

Serious adverse events are defined as any untoward medical occurrence that at any dose:

- result in subject's death.
- are life-threatening.
- result in permanent or significant disability/incapacity.
- cause hospital admission or prolong hospital stay.
- result in congenital anomalies or birth defects.
- medically important condition that may jeopardize the subject or may require intervention to prevent any of the outcomes listed above. Examples of such events are intensive treatment in an emergency room or at home for allergic bronchospasm; blood dyscrasias,

Amendment 04, Final Version 1.0
Protocol No.: BB-2001-201b
EudraCT No.: 2017-000877-35
Amendment 04, Final Version 1.0
07/Nov/2018
Page 74 / 142

or convulsions that do not result in hospitalisation; or development of drug dependency or drug abuse.

NOTE: The term "life-threatening" in the definition of "serious" refers to any adverse event that places the subject, in the view of the investigator, at immediate risk of death from the event as it occurred, i.e., it does not include an event that, had it occurred in a more severe form, might have caused death.

An overnight stay in the hospital that is only due to transportation, organisation or accommodation problems and without medical background does not need to be handled/documented as a SAE. Hospitalisations due to surgical procedures for pre-existing conditions that have been planned before enrolment of the subject are not considered SAEs.

# 9.1.4 Unexpected Adverse Event

Any adverse event, which is not described in the Reference Safety Information (RSI) of the Investigator Brochure (IB) in nature, severity or frequency is unexpected. Expectedness will be assessed in relation to the RSI of the IB. For details, please check the IB version 9, 2017.

### 9.1.5 Suspected Unexpected Serious Adverse Reaction (SUSAR)

A Suspected Unexpected Serious Adverse Reaction (SUSAR) is a suspected adverse reaction related to the treatment that is both unexpected and serious.

#### 9.2. Adverse Event Severity

Severity of adverse events will be classified according to the following criteria:

Mild Trivial adverse events, of low significance and short duration that

require no special treatment, and do not substantially impair the

normal life of the subject.

Moderate Adverse events causing enough discomfort to interfere with normal

life of the subject but are usually ameliorated by simple therapeutic

measures.

Severe Adverse events causing disability to work or perform the daily

activities of the subject, and require systemic drug therapy or other

treatment

#### 9.3. Relationship to Study Drug

The causal relationship of an adverse event with the study medication will be established based on the following definitions:

**Unrelated** There is little or no chance that the study medication caused the AE;

other conditions, including concurrent illnesses, progression or expression of the disease state, or a reaction to a concomitant

medication best explain the event.

Amendment 04, Final Version 1.0
Protocol No.: BB-2001-201b
EudraCT No.: 2017-000877-35
Page 75 / 142

**Unlikely** Event of laboratory test abnormality, with a time to drug intake that

makes a relationship improbable (but not impossible). Disease or

other drugs provide plausible explanations.

**Possible** A reasonable temporal association exists between the AE and

treatment administration **and/or** the AE follows a known response pattern to the study drug; **but** could have been produced by other factors such as the subject clinical state, therapeutic intervention or

concomitant therapy.

**Probable** A reasonable temporal association exists between the AE and

treatment administration **and/or** the AE follows a known response pattern to the study drug; **and** could not have been produced by other factors such as the subject clinical state, therapeutic intervention or

concomitant therapy.

**Definite** A definite temporal association exists between the AE and treatment

administration and/or the AE follows a known response pattern to the study drug; and could not have been produced by other factors such as the subject clinical state, therapeutic intervention or concomitant therapy, and the event either occurs immediately following study drug administration or abates following discontinuation of study treatment and may be confirmed by

reappearance on repeat exposure.

For the purpose of safety analyses, all AEs which are classified as 'Possible' or 'Probable' or 'Definite' will be considered treatment-related events.

Any subject who is withdrawn from the study because of an AE will be followed until the outcome of the event is determined, and the investigator will prepare a written summary of the event and document the available follow-up information on the eCRF.

# 9.4. Action Concerning Study Medication

- Drug withdrawn a study medication is stopped due to the particular AE.
- Dose not changed the particular AE did not require stopping a study medication.
- Unknown only to be used if it has not been possible to determine what action has been taken.
- Not Applicable a study medication was stopped for a reason other than the particular AE e.g., the study has been terminated, the subject died, dosing with study medication was already stopped before the onset of the AE.
- Dose Interrupted the dose was interrupted due to the particular AE.

#### 9.5. Outcome

- Recovered/Resolved Subject returned to first assessment status with respect to the AE/PTE.
- Recovering/Resolving the intensity is lowered by one or more stages: the diagnosis or signs/symptoms has almost disappeared; the abnormal laboratory value improved, but

Amendment 04, Final Version 1.0 07/Nov/2018 Page 76 / 142

has not returned to the normal range or to baseline; the subject died from a cause other than the particular AE/PTE with the condition remaining "recovering/resolving".

- Not recovered/not resolved there is no change in the diagnosis, signs or symptoms; the
  intensity of the diagnosis, signs/ symptoms or laboratory value on the last day of the
  observed study period has got worse than when it started; is an irreversible congenital
  anomaly; the subject died from another cause with the particular AE/PTE state remaining
  "Not recovered/not resolved".
- Resolved with sequelae the subject recovered from an acute AE/PTE but was left with permanent/significant impairment (e.g., recovered from a cardiovascular accident but with some persisting paresis).
- Fatal the AEs/PTEs which are considered as the cause of death.
- Unknown the course of the AE/PTE cannot be followed up due to hospital change or residence change at the end of the subject's participation in the study.

#### 9.6. Adverse Event Collection Period

Adverse events will be collected throughout the whole study period (screening of 3 weeks, baseline of 1 week, treatment period of 6 weeks and safety follow-up of 4 weeks).

A safety follow-up call will be performed 4 weeks after subject's discharge at the end of the treatment period. Information regarding any ongoing AEs, new AEs and SAEs and concomitant medications will be collected. Subjects who completed the treatment who cannot be contacted for this follow-up call will be considered to have completed the study. Documentation of unsuccessful follow-up phone contact, after 3 attempts, should be included in the subject's source document.

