### Follow-up Period (+Day $28 \pm 2$ )

During the following up period the eye examination post dose on Day 42 will be conducted and a follow-up safety visit will be performed 28 days after the last IMP administration where the vital signs (including heart rate and blood pressure), C-SSRS, HAM-D, and BPRS+ will be assessed. The eye examination should be performed before the follow up visit. Additional unscheduled visits may be arranged as needed for the management of eye examination findings and / or adverse event findings.

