#### 18.15. Schedule of Assessments

VISITS Week	Screening period (W-4)	Baseline period (W-1)	Randomisation Visit 1	Treatment Visit 2 (W2)		Treatment Visit 3 or Early Term (W6)	FUP (1)
Study days (referred to D1 [Day of first administration]	D-28 to D-8	D-7 to D-2	D-1	D14 (± 2)	D35	D42 (± 3)	+D28 (± 2)
(allowed deviation days in brackets)							
Informed consent	X						
Inclusion and exclusion criteria	X	$X^{(3)}$	X 				
Demographics	X						
Medical history and previous medication	$X^{(4)}$	X					
Concurrent Medical Condition	X						
Physical examination	X					X	
Vital signs (including heart rate and blood pressure)	X			X		X	X
Pregnancy test	X		X 			X	
Laboratory tests	X	X 				X	
Pharmacogenomic blood sample	X 						
Electrocardiogram	X					X	
Eye examination	X					X 	
Epworth Sleepiness Scale (ESS)	X		X	X		X	
Scales for Outcome in Parkinson's Disease Sleep (SCOPA-Sleep)			X	X		X	
Parkinson's Disease Sleep Scale (PDSS-2)			X	X		X	
Fatigue Severity Scale (FSS)	X					X	
Berlin Questionnaire (BQ)	X						
Unified Parkinson's Disease Rating Scale (UPDRS Part III) 			X	X		X	
Cognitive Impairment (Montreal Cognitive Assessment – MoCA	X					X	
Hamilton Rating Scale for Depression (HAM-D) $^{(10)}$	X			X		X	X
Columbia-Suicide Severity Rating Scale (C-SSRS) (10)	X			X		X	X
Brief Psychiatric Rating Scale positive subscale (BPRS+) 	X			X		X	X
Maintenance of Wakefulness Test (MWT) 		X				X	
Polysomnography 		X				X	
Free living activity (GENEActiv ®)(2)		X	X		X	X	
Randomisation			X				
Treatment intake 				X	X	X	
Adverse Events		X	X	X	X	X	X
Concomitant medication		X	X	X	X	X	

- (1)All subjects will perform a safety follow-up visit 28 days after last study visit performed.
  - Additional unscheduled visits may be arranged in case of eye examination, ECG, or adverse event findings.
- (2) GENEActiv® to be worn for 7 days continuously on the non-dominant hand day -7 to day -1 at baseline and before the last dose, day 35 to day 42.
- (3) Inclusion / Exclusion criteria to be reconfirmed before randomisation
- (4) Prohibited medical history will be assessed 4 weeks before Screening D-28
- (5) Dipstick pregnancy test to be completed before randomisation
- (6) If there are more than 14 days between screening and baseline

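### The 4-week safety follow-up is a phone call in protocol sections 9.1.1 and 9.6 but a visit with vital signs, C-SSRS, HAM-D and BPRS+ in section 8.4.2 and the schedule; the passages must be reconciled

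*Protocol*

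**What the plan says.** Two places in protocol section 9 make the 4-week safety follow-up a telephone contact.

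- Section 9.1.1 covers all subjects, expressly including those who withdraw, and follows them up "by means of a phone call 4 weeks after the end of the study treatment".
- Section 9.6 says "A safety follow-up call will be performed 4 weeks after subject's discharge at the end of the treatment period". On content it says "Information regarding any ongoing AEs, new AEs and SAEs and concomitant medications will be collected", and it names no rating scale and no vital signs. Treatment completers who "cannot be contacted for this follow-up call will be considered to have completed the study"; three failed attempts are to be documented in the source record.

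Section 8 and the schedule describe an attended contact.

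- Section 8.4.2, Follow-up Period: "a follow-up safety visit will be performed 28 days after the last IMP administration". Vital signs are taken there, and "C-SSRS, HAM-D, and BPRS+ will be assessed".
- Section 8.4 also calls it a visit. Section 8.4.1.7 places vital signs at follow-up, and sections 8.4.1.15.3, 8.4.1.15.4 and 8.4.1.15.5 place HAM-D, C-SSRS and BPRS+ at a follow-up visit.
- Appendix 18.15, footnote 1: "All subjects will perform a safety follow-up visit 28 days after last study visit performed". The FUP column is marked for vital signs, the three scales and adverse events.

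The word call also remains in two places within this second group: the eye-examination line under Visit 3 in section 8.4.2, and footnote 8 of the schedule.

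**The concern.** The follow-up values feed named endpoints. Section 6.2.2 extends HAM-D change, C-SSRS findings and BPRS+ findings to the safety follow-up. SAP section 10.2 lists a HAM-D analysis at follow-up, and the titles of SAP sections 12.2 and 12.3 carry C-SSRS and BPRS+ incidence to the same point. Section 7.2 explains why the scales are there: patients with Parkinson's disease have a higher risk of psychosis and depression than the general population.

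For subjects who complete treatment, this contact is the only scheduled measurement of the three scales after dosing ends. Section 9 is the adverse-event section, so staff responsible for safety follow-up could reasonably work from it. If they did nothing more than it lists, these values would not exist and could not be recovered later.

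**Working it through.** The plan states no figure to reproduce. The check is a comparison of current text in one protocol version, with some simple arithmetic.

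**1. Content.** Of the four assessments named in section 8.4.2 (vital signs, C-SSRS, HAM-D, BPRS+), section 9.6 lists 0 of 4. Conversely, the Follow-up Period paragraph of 8.4.2 does not mention adverse events or concomitant medication. The schedule's FUP column marks adverse events and, as far as the table can be read, not concomitant medication. No single place gives the full content.

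**2. Use of the data.** Each of the three scales has four scheduled time points: screening, Visit 2, Visit 3 or early termination, and follow-up. Without the last, 1 of 4 is lost.

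- HAM-D: SAP section 10.2 analyses the follow-up change by ANCOVA. The SAP describes imputation of missing scores only for ESS (sections 9.1, 9.2.1 and 10.4.2), and its re-allocation windows (section 4.1) cover only Visits 2 and 3. Read literally, a subject without the follow-up HAM-D leaves that analysis.
- C-SSRS: SAP section 12.2 reports Visit 2, Visit 3 and an overall figure, with no separate row for the follow-up visit. An affected subject still counts at weeks 2 and 6, and is observed for a shorter time in the overall figure.
- BPRS+: SAP section 12.3 reports change at each corresponding visit; the follow-up value is missing.
- ESS: not scheduled at follow-up, so the primary analysis is untouched.

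**3. Scale of a misreading.** Section 7.1 gives approximately 230 subjects and around 48 sites. Assuming even recruitment, 230 / 48 = 4.8 subjects per site, and 1 / 48 = 2.1% of the follow-up data per site that used section 9 alone. Recruitment is competitive, so actual sites will vary. The number of such sites is unknown and could be zero.

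**4. Completion status.** Section 9.6 counts a treatment completer who cannot be contacted as having completed the study. The failed attempts go into the source record, but the count of completers does not change, so disposition would not reveal the missing follow-up.

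**5. Starting point of the 28 days.** Five are given:

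- last IMP administration (8.4, 8.4.1.15.3 to 8.4.1.15.5, 8.4.2);
- end of study treatment (9.1.1);
- discharge at the end of the treatment period (9.6);
- last study visit (18.15, footnote 1);
- Visit 3 or the early termination visit (SAP section 9.2.7).

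Take a completer whose last dose is on Day 42, with Visit 3 at Day 42 ± 3. With the ± 2 window, last dose gives Day 42 + 28 = 70, window 68 to 72. A Visit 3 on Day 45 gives Day 73, window 71 to 75. Days 71 and 72 satisfy both.

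For an early terminator, let the termination visit fall g days after the last dose L. The windows are L + 26 to L + 30 and L + g + 26 to L + g + 30. A contact timed exactly to one falls outside the other when g > 2, and no day satisfies both when g > 4. The documents do not fix g.

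Section 7.1 also asks for at least 4 weeks after completion of the treatment period, whereas 28 − 2 = 26 days is within the 8.4.2 window.

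**The case against.** The strongest reply is that the protocol says where to look. Section 8.4 names a follow-up visit and states that it describes the activities of all study visits; 8.4.1, 8.4.2 and the FUP column agree on the assessments. Section 9.6 is about adverse-event collection, so it naturally lists adverse-event data. It does not say that nothing else is collected, and no passage permits omitting the scales. The Amendment 03 change log records a move from call to visit, so the section 9 wording looks like a remnant.

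Most of this stands, and it is why the loss is conditional. It does not remove the contradiction. Section 9 states a different mode of contact, and the schedule itself says visit in footnote 1 and call in footnote 8, so preferring the schedule does not fully settle the matter.

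A reader might infer more than the documents support:

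- That the off-treatment data will be lost. Only a site doing nothing beyond section 9 would lose them, and most of the text points sites to the visit.
- That withdrawn subjects are singled out for a weaker follow-up. Section 9.1.1 covers all subjects and mentions withdrawals as included. The documents do not say that withdrawn subjects are at greatest risk, and early terminators should also have the Visit 3 procedures, which include the three scales.
- That anyone not reached counts as complete. The rule applies only to subjects who completed treatment, and appears in 9.6 but not in 9.1.1.
- That the differing clocks disturb the whole trial. For completers the difference is about 3 days.

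**Conclusion.** The inconsistency is real and sits in operative text. At a site that did only what section 9 lists, 0 of 4 follow-up assessments would be collected. Its subjects would leave the HAM-D follow-up analysis and contribute no follow-up C-SSRS or BPRS+ data: about five subjects per such site, assuming even recruitment and no imputation beyond ESS. A site following 8.4.2 and the schedule loses nothing. How many sites would misread the protocol cannot be estimated from the documents.

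The 9.6 completion rule would keep any such gap out of disposition. The differing starting points matter mainly for early terminators. The primary ESS result is not affected. The point should be corrected because prespecified safety data and one time point of a secondary endpoint depend on it and the correction is cheap; it does not put the trial's main conclusion in doubt.

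**What to change.** Reconcile protocol sections 9.1.1 and 9.6, the Visit 3 eye-examination line in 8.4.2 and footnote 8 of 18.15 with protocol sections 7.1, 8.4, 8.4.1.7, 8.4.1.15.3 to 8.4.1.15.5, the Follow-up Period in 8.4.2, footnote 1 and the FUP column of 18.15, and SAP section 9.2.7. Four items should be the same wherever the follow-up is mentioned:

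- mode of contact;
- content, including where adverse events and concomitant medication are recorded;
- the event from which the 28 days run, with its window;
- what counts as a completed follow-up, as distinct from completed treatment.

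Which procedure applies is for the sponsor to decide. The cost is protocol and SAP wording and a clarification to sites; sample size and the primary analysis do not change.
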